**Methods:** Following baseline assessment, participants will be randomized to BWTraining at 2 months (Immediate group) or 1-year post-stroke (Delayed group). The intervention consists of 18 sessions (3X/week for 6 weeks) of BWTraining: 20–30 minutes of step training using a Body Weight Support and Treadmill system (BWST) followed by 15 minutes of overground gait training delivered by a physical therapist-led team. Participants will walk backward overground with assistance as warranted to transfer stepping skills from the BWST environment to overground. The Immediate group will be followed prospectively for 1-year and compared to the Delayed group to determine the effectiveness of BWTraining in decreasing falls (Specific Aim#1). BWSpeed post-intervention will be compared between groups to assess the timing effect of BWTraining (Specific Aim #2). The Delayed group will be followed prospectively for 1-year prior to BWTraining, to determine if BWSpeed at 2-months is a predictor of fall incidence in the first year post-stroke (Specific Aim #3).

Outcome Measures: Fall incidence 2-months to 1-year post-stroke is our primary outcome measure. Secondary measures include forward and backward walking gait speed, dynamic balance measured by the Functional Gait Assessment, fall self-efficacy measured by the Activities-Balance Confidence Scale and gait kinematics.

Data Analysis Plan: The total number of falls per patient month for the immediate and delayed intervention groups will be calculated, and using a nonparametric ratio estimate, point and interval estimates for the average hazard for each group will be determined. The ratio of the two individual group estimates, 95% confidence limits and P-values will be obtained. Forward stepwise ordinal logistic regression will be used to determine the independent relationship between BWSpeed at 2-months post-stroke and 1-year fall incidence of those in the Delayed intervention group.

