**Fall Incidence.** In addition to the assessments described above that will be conducted at the 5 specific time points, fall incidence will be monitored throughout the study for each participant using the international standards for defining and reporting falls, including the following definition for a fall: “A person has a fall if they end up on the ground or floor when they did not expect to. Most often a fall starts while a person is on their feet, but a fall could also start from a chair or bed. If a person ends up on the ground, either on their knees, their belly, their side, their bottom, or their back, they have had a fall.” This explanation will be provided to participants and caregivers and printed on monthly calendars issued at randomization. Participants and/or caregivers will place an “X” on the corresponding date if a fall occurs, and submit to their study site each month (even if no falls occurred). If a calendar is not received within one week of its expected return, study personnel will contact participants. Participants will be contacted to follow-up on reported falls using the Fall Characterization Questionnaire. Information collected for each fall will include presence and nature of any injury, location of the fall, and ability to get up independently after the fall. Three categories will be used to characterize falls outcome poststroke: multiple or injurious (M/I); single, noninjurious (S/NI); and nonfallers. Injurious falls will be defined as those resulting in serious injury: fracture, loss of consciousness, or hospital admission. This information will be collected in-person for those currently receiving the study intervention and via phone for participants who have either completed or have yet to begin BWTraining.

**Monitoring Delayed BWTraining.** Participants randomized to Delayed BWTraining (Usual Care) will be assessed at the same time points as the Immediate BWTraining Group, at Baseline (Assessment A), at 6-weeks post-enrollment (Assessment B) and at 6-months post-stroke (Assessment C). In addition to these on-site assessments, this group (as well as the Immediate BWTraining Group) will be monitored throughout the first year post-stroke for 1) Any usual and customary rehabilitation services and 2) Fall incidence.

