Data Analysis Plan: For Specific Aim #1 (primary outcome for entire study is the average fall rate per year), we will calculate the total number of falls per patient year for the Immediate intervention and Delayed intervention (control) groups, and use the actuarial method described below to estimate the average hazard rate in each group, and the overall hazard ratio. We will compare the Immediate and Delayed groups' fall rate at Assessment D, 1-year post-stroke. The analysis takes repeated falls within the same subject into account. Consider the number of falls,  $Y_{ij}$  for the  $j$ -th patient on treatment  $i$  ( $i=1,2$ ) in the year, and  $T_{ij}$ , the time at risk for the subject (usually 1 year, less for withdrawals before then). The estimated average fall hazard for treatment  $i$  is the ratio estimator  $H_i = \sum Y_{ij} / \sum T_{ij}$ . Under nonparametric considerations, if the true average hazard over subjects and time for treatment  $i$  is  $\Theta_i$ , then by the delta method,  $\text{Log}(H_i) - \text{log}(\Theta_i)$  ( $\text{Log}=\text{natural log}$ ) is asymptotically normal with mean zero and variance  $V_i$ ,  $i=1,2$  defined by

$$V_i = \{ \{ \text{Var}(Y_{ij}) / (\text{Mean } Y_{ij})^2 \} + \{ \text{Var}(T_{ij}) / (\text{Mean } T_{ij})^2 \} - 2 \text{Cov}(Y_{ij}, T_{ij}) / (\text{Mean } Y_{ij}) / (\text{Mean } T_{ij}) \} / N_i$$

with the means, variances, and covariance, the sample moments, and  $N_i$  is the sample size for treatment  $i$ . The log of the estimated average hazard ratio  $\text{Log}(H_2/H_1)$  is asymptotically normally distributed with mean  $\text{Log}(\Theta_2 / \Theta_1) = \text{Log}(\Theta_2) - \text{Log}(\Theta_1)$  and asymptotic variance  $(V_1 + V_2)$ . This enables us to obtain a two-sided P-value and after taking natural anti-logs, a point estimate and 95% confidence interval for the true average hazard ratio.

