*Power analysis:* The study is powered around Specific Aim 1, comparison of fall incidence at 1-year post-stroke for those in the Immediate versus the Delayed BWTraining groups. Although the analysis is valid for any within patient distribution of the number of falls and time at risk, we must make additional assumptions to calculate power. Dean and colleagues, in a study of post-stroke fall incidence reported an average of 1.5 falls per patient year, and hence we will plan for a 33% reduction from 1.8 falls per year to 1.2 falls per year, with 80% power at  $p=0.05$ . Using a Poisson rate of 1.8 vs. 1.2 falls per year we would require 64 subjects randomized to each group to be followed for one year. Although all data for withdrawals will be used up to the time of withdrawal, we shall recruit an additional 14 subjects (142 total) to assure we observe 128 patient years. We expect the actual distribution of falls to be more compact (less variable) than the Poisson, which allows unlimited falls for a patient. This suggests the real variance within a group will be lower than that suggested in the Poisson, making power a bit higher than stated here. We cannot quantify this, however. Power was derived via large sample approximations, and verified via 10,000 simulations.

All hard copy records will be stored in a locked filing cabinet in a locked office accessible only to study personnel. All electronic data will be stored on a VA secured server. Hard copy data collected at Brooks Clinical Research Center will be transported to the Gainesville VA BRRC via the Principal Investigator in a locked briefcase.

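### On the nominal schedule, 142 participants give at most 118 patient-years for the primary comparison, not the assured 128, a loss of about 3 points of power at best

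*Combined protocol and SAP*

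**What the plan says.** The power analysis (section 6, Research Plan) plans for a Poisson rate of 1.8 vs 1.2 falls per year with 80% power. It requires "64 subjects randomized to each group to be followed for one year", and adds that "we shall recruit an additional 14 subjects (142 total) to assure we observe 128 patient years". The Data Analysis Plan in the same section defines T_ij as "the time at risk for the subject (usually 1 year, less for withdrawals before then".

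Other places fix when the counting starts and stops:

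- **Outcome (section 3, Outcome Measures):** "Fall incidence 2-months to 1-year post-stroke is our primary outcome measure".
- **Start:** the fall definition is "printed on monthly calendars issued at randomization" (section 6, Fall Incidence). Inclusion criterion 2 admits people from 2 to 4 months after stroke.
- **End:** the Data Analysis Plan compares the groups' "fall rate at Assessment D, 1-year post-stroke". The opening of section 6 also names Assessment D as the primary endpoint for Aim 1. Under Monitoring Delayed BWTraining, both groups "will be monitored throughout the first year post-stroke" for falls.
- **Control period:** the Delayed group starts its training at 1 year post-stroke (section 6, after the consent paragraph).

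Two places use one-year wording that does not fit these dates. The Abstract's Methods has each group followed for one year, in the Delayed group's case before its training. Hypotheses 1a and 1b speak of the year following training at 2 months.

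**The concern.** Assessment D is dated from the stroke, but the time at risk starts at randomisation, 2 to 4 months later. The power analysis treats the two as the same and credits each completer with 12 months. This paragraph is the only sample-size basis for the primary aim. If the credited exposure is not available, the patient-year target and the stated power are both too high. The 14 extra recruits, meant to cover attrition, would then be partly or wholly used up by the shorter window.

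**Working it through.** **Inputs.** Power analysis: rates 1.8 and 1.2 per year, Poisson, 80% power, alpha 0.05, 64 per group, 142 recruited. Data Analysis Plan: two-sided test. Opening of section 6: attrition up to 10%. Entry at 2 to 4 months; Assessment D at 12 months post-stroke. One assumption is added: the fall rate is constant over the window, since the documents give no time pattern.

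**Formulas**, with m = patient-years per arm:

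1. Log rate ratio, unpooled: Φ( ln 1.5 × √m / √(1/1.8 + 1/1.2) − 1.96 )
2. Log rate ratio, pooled null variance: Φ( [ln 1.5 × √m − 1.96 × √(2/1.5)] / √(1/1.8 + 1/1.2) )
3. Rate difference: Φ( 0.6 × √(m/3.0) − 1.96 )
4. Event-based (Schoenfeld): Φ( ln 1.5 × √(d/4) − 1.96 ), where d = 3.0 × m expected falls

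**Reproducing the plan's figure.** For 80% power, formulas 1 to 3 need 66.3, 64.4 and 65.4 patient-years per arm. Formula 4 needs 191 falls, against 3.0 × 64 = 192 expected. The stated 64 per group and 80% are therefore reproduced for one full year each.

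**Exposure available.** Entry at 2 months leaves 12 − 2 = 10 months; entry at 4 months leaves 8. The ceiling is 142 × 10/12 = 118.3 patient-years. Reaching 128 would need a mean of 128/142 × 12 = 10.8 months each, longer than the longest nominal window.

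**Power at both exposures.**

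| Method | 128 patient-years (m = 64) | 118.3 patient-years (m = 59.2) |
|---|---|---|
| 1. Log ratio, unpooled | 78.6% | 75.4% |
| 2. Log ratio, pooled | 79.7% | 76.6% |
| 3. Rate difference | 79.1% | 76.0% |
| 4. Schoenfeld | 80.2% | 77.1% |
| Simulation of the plan's ratio estimator and V_i | about 79% | about 76% |

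Within each row the loss is about 3 points. Expected falls drop from 128 × 1.5 = 192 to 118.3 × 1.5 = 178.

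**Sensitivity cases**, illustrative because the documents give neither an entry distribution nor withdrawal times (ranges span formulas 1 to 4):

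| Case | Patient-years | Power |
|---|---|---|
| 142 enter at 2 months, 14 leave halfway | (128 + 14/2) × 10/12 = 112.5 | 73–75% |
| 128 people at 10 months, dropouts contribute nothing | 128 × 10/12 = 106.7 | 71–73% |
| 142 all enter at 4 months, none leave | 142 × 8/12 = 94.7 | 66–68% |

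**The case against.** **Follow-up could mean 12 months from randomisation.** The one-year wording in the Abstract and in Hypothesis 1a allows this, and falls are monitored throughout the study. But that window would end 14 to 16 months post-stroke, after the Delayed group has started the same training. It would also contradict the Data Analysis Plan, which places the comparison at Assessment D. The reading does not rescue the figure.

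**The variance may be smaller than assumed.** The plan says "We expect the actual distribution of falls to be more compact (less variable) than the Poisson", but adds that it cannot quantify this. Restoring 80% at the ceiling would need a variance of about 0.89 to 0.93 times Poisson, depending on the formula (118.3 divided by 132.6, 130.8, 128.9 or 127.3 patient-years). That is possible, but the documents do not show it, and overdispersion would work the other way.

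**The shortfall is modest and rests on nominal dates.** This stands. The gap is 10.8 against 10 months, about 25 days per person, and the documents give no visit window for Assessment D. A reader might infer that 128 patient-years are impossible under any circumstances. The text supports that only for visits held on their nominal dates.

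**The analysis itself is unaffected.** This also stands. The estimator divides total falls by actual time at risk, so a shorter window does not bias the rate ratio or invalidate the test or interval.

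**Conclusion.** The statement that 142 recruits assure 128 patient-years is wrong on the plan's nominal schedule. The ceiling is 118 patient-years, with power of about 75–77% by standard formulas and about 76% when the plan's own estimator is simulated. This rests on Poisson rates of 1.8 vs 1.2 per year, constant over the window, two-sided 0.05 and equal arms. Compared like for like, the best-case loss is about 3 points.

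Two stronger readings are tempting but not supported. One is a loss of 4 to 5 points against the stated 80%. That mixes methods, because it sets formulas giving 78.6–79.1% at 128 patient-years against a figure that other standard formulas reproduce. The other is that the trial's power is about 70%. That depends on entry and withdrawal patterns the documents do not give. What can be said is that the ceiling already uses the whole attrition allowance and assumes no entry after 2 months, so the realised figure is likely to be lower.

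**What to change.** 1. Define the primary window once: from randomisation to the participant's own Assessment D (1 year post-stroke), before any Delayed training. Reconcile with it the one-year follow-up wording for both groups in the Abstract's Methods and the next-year wording in section 5.
2. In the Data Analysis Plan, describe T_ij as the actual time from randomisation to Assessment D, about 8 to 10 months, less for withdrawals.
3. In the power analysis, keep 64 per group for one year as the input to the plan's calculation, because that assumption produces the number. Replace the assurance of 128 patient-years with at most 118, and restate power as at most about 75–77% under the stated Poisson assumptions.
4. The sponsor should rerun its own calculation and its 10,000 simulations with the 8 to 10 month window and 10% attrition, and report the resulting lower figure with its entry and withdrawal assumptions.

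The cost is protocol wording and one rerun of the planning calculation; no new participants, visits or analyses are needed. Whether to accept the lower power or restore the exposure is a separate decision for the sponsor. For scale, 128 patient-years at 10 months each would take 128/(10/12) = 153.6, about 154 completers.

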## **5. Specific Aims:**

**Aim #1:** Test the hypothesis that 1-year fall incidence is decreased for participants randomized to BWTraining administered at 2-months post-stroke (versus usual care comparison group).

**Hypothesis #1a:** BWTraining at 2-months post-stroke reduces the number of falls over the next year.

**Hypothesis #1b:** BWTraining at 2-months post-stroke increases gait speed, improves balance and increases balance confidence over the next year.

**Aim #2:** Test the hypothesis that BWTraining at 2 months (immediate) vs. 1-year (delayed) post-stroke is more effective at improving BWSpeed.

**Hypothesis #2a:** BWSpeed improvement from 2- to 14-months post-stroke is greater when BWTraining is delivered at 2 months versus 1 year post-stroke.

**Hypothesis #2b:** Improvements in forward gait speed, Functional Gait Assessment and Activities-Balance Confidence Scale from 2- to 14-months post-stroke are greater when BWTraining is delivered at 2 months versus 1 year post-stroke.

**Aim #3:** This exploratory aim will test the hypothesis that BWSpeed at 2-months post-stroke is a significant predictor of fall incidence over the next year 1 year period, after adjusting for other covariates.

**Hypothesis #3:** BWSpeed at 2-months will be a significant predictor of fall incidence during the first year post-stroke, after adjusting for other covariates.

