Three-Meter Backward Walk Test. We will use this test to collect our variable of interest, BWSpeed. The test consists of a 1 meter warm-up distance, a timed 3 meter distance, followed by an additional 1 meter to continue walking. Participants will walk this distance two times and the speed will be averaged.

Functional Gait Assessment (FGA). a 10-item clinical gait and balance test during which participants perform the following activities: walk at normal speeds, at fast and slow speeds, with vertical and horizontal head turns, with eyes closed, over obstacles, in tandem, backward and while ascending and descending stairs. Excellent test-retest and intra- and inter-rater reliability has been established patients post-stroke.

Activities-Specific Balance Confidence Scale (ABC): This 16-item self-report measure is used to assess perceived efficacy (self-reported confidence) in maintaining balance while performing a number of activities common in community-dwelling older adults.

Berg Balance Scale (BBS): This tool consists of 14 items that assesses static and dynamic standing balance, ability to sit, stand up and transfer. From our previous work characterizing and identifying risk factors for falls post-stroke, BBS scores  $\leq 42/56$  was the single best predictor of multiple/injurious falls. This assessment is ubiquitously used in stroke rehabilitation and will aide in describing our study cohort. This has been tested in a stroke population and has well-established reliability and validity.

Lower-Extremity Fugl-Meyer Motor Score: This tool consists of 17 items that assess motor control of the lower extremity as participants move their hip, knee and ankle in lying, sitting and standing is probably the most widely known scale of motor and sensory recovery after stroke. This assessment will provide a description of lower extremity impairment and aide in describing our study cohort.

Four-Step Square Test: This clinical test of dynamic standing balance examines the ability to step over small objects, change direction and includes taking a backwards step. In a

study that confirmed the feasibility and validity of this assessment for individuals post-stroke, those who reported a fall scored > 15 sec to complete the assessment.

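### The plan says power exceeds 80% because falls vary less than Poisson; the reason given adds no power, and differences in fall risk between patients would reduce it

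*Combined protocol and SAP*

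**What the plan says.** The Power analysis paragraph of section 6 plans for a one-third reduction, from 1.8 to 1.2 falls per year, with 80% power at the 0.05 level. It assumes Poisson counts, 64 patients per group and one year of follow-up. Recruitment is raised to 142 so that 128 patient-years are observed.

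On the choice of distribution it says: "We expect the actual distribution of falls to be more compact (less variable) than the Poisson, which allows unlimited falls for a patient". From this it infers a smaller within-group variance, "making power a bit higher than stated here", and adds that the gain cannot be quantified. No variance, dispersion estimate or sensitivity analysis is given, and variance above Poisson is not considered.

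The primary analysis (section 6, Data Analysis Plan) compares log fall rates using a delta-method variance, "with the means, variances, and covariance, the sample moments". The test is two-sided ("This enables us to obtain a two-sided P-value").

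Elsewhere the documents expect patients to differ in fall risk. Section 5 hypothesises that "BWSpeed at 2-months will be a significant predictor of fall incidence during the first year post-stroke". The Abstract plans to estimate the "independent relationship between BWSpeed at 2-months post-stroke and 1-year fall incidence of those in the Delayed intervention group", so the differences are sought among enrolled patients. The Berg Balance Scale entry in section 6 reports that a score of 42 or less "was the single best predictor of multiple/injurious falls".

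**The concern.** The only argument for variance below Poisson is that a Poisson count has no upper limit. At a mean below 2 the upper tail is almost empty, so removing it changes nearly nothing.

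The usual departure from Poisson in fall counts goes the other way. If each patient's counts are Poisson given that patient's own rate, then Var(Y) = mean + Var(rate), which exceeds the Poisson variance whenever rates differ. Because the planned standard error comes from sample variances, that extra variation keeps the test asymptotically valid but reduces its power.

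Readers are therefore told that the stated power for the primary aim errs on the low side, when it holds only if all patients in a group share one fall rate. A non-significant result could then be read as evidence against the training when the trial had limited power for the planned reduction.

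**Working it through.** **Inputs.** From section 6: rates 1.8 and 1.2 per year, one year at risk, 64 per group (71 if all 142 recruits complete), two-sided 0.05. Assumed, because the documents give no value: negative binomial dispersion *a*, so that Var(Y) = mean + *a* × mean².

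**1. The plan's own figure.** On the scale of the planned test, the variance of the log rate ratio under Poisson is (1/1.8 + 1/1.2)/n = 1.389/64 = 0.0217, so SE = 0.1473. With ln(1.5) = 0.4055, power = Φ(0.4055/0.1473 − 1.96) = 78.6%. Simulating the planned test (40,000 runs) gives 79.3%. Sample size for 80% power is 65 per group on the square-root scale, 66 on the rate difference and 67 on the log ratio. The plan's 64 is therefore reproduced closely under pure Poisson counts.

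**2. The reason given.** At a mean of 1.8, P(more than 8 falls) = 0.00011. Capping counts at 8 moves the variance from 1.800 to 1.798. Power at 64 per group:

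| Cap on falls | none | 10 | 8 | 6 | 5 | 4 |
|---|---|---|---|---|---|---|
| Power, % | 78.6 | 78.6 | 78.6 | 78.6 | 78.4 | 77.6 |

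A tight cap also shrinks the difference in means, so power drifts down.

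**3. Differences in risk between patients.** The variance of the log rate ratio becomes (1/1.8 + 1/1.2 + 2*a*)/n. For *a* = 0.25 this is 1.889/64 = 0.0295, SE = 0.1718, and power = Φ(0.4055/0.1718 − 1.96) = 66%. Patients per group for 80% power = 7.849 × (1.389 + 2*a*)/0.1644, where 7.849 = (1.960 + 0.842)² and 0.1644 = ln(1.5)². The detectable ratio holds the control rate at 1.8.

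| Dispersion *a* | 0 | 0.05 | 0.1 | 0.25 | 0.5 | 1 | 2 |
|---|---|---|---|---|---|---|---|
| Power, 64 per group, % | 79 | 76 | 73 | 66 | 56 | 42 | 29 |
| Power, 71 per group, full year, % | 83 | 80 | 77 | 70 | 60 | 46 | 31 |
| Per group for 80% power | 67 | 72 | 76 | 91 | 115 | 162 | 258 |
| Detectable rate ratio, 64 per group | 0.66 | 0.65 | 0.64 | 0.61 | 0.57 | 0.51 | 0.43 |

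The planned ratio is 0.67. A dispersion of 0.25 means patient rates with a coefficient of variation of √0.25 = 50%. Simulating the planned estimator with its sample variances (20,000 runs, 64 per group) gives 73.1, 65.9, 56.6, 43.3 and 30.0% for *a* = 0.1, 0.25, 0.5, 1 and 2, in line with the formula. Simulated type I error at 1.5 in both groups is 0.051 for *a* = 0 and 0.057 for *a* = 1.

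**4. Could more regular counts within a patient cancel this?** Let the within-patient variance be φ times Poisson. Cancelling requires φ = 1 − 2*a*/1.389, which is 0.64 for *a* = 0.25 and 0.28 for *a* = 0.5. It reaches 0 at *a* = 0.69, beyond which no cancellation is possible.

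**5. Illustration only.** Under Poisson, the mean of 1.5 falls per year cited in section 6 implies 1 − exp(−1.5) = 78% fallers; the Abstract gives 40% to 70%. Solving (1 + 1.5*a*)^(−1/*a*) = 1 − P(faller) gives *a* = 0.35 for 70% fallers (power 61%) and *a* = 1.0 for 60% (power 42%). The two figures come from different sources, so this indicates a direction and does not estimate the dispersion.

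**The case against.** The strongest points on the other side are these.

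- **No dispersion value is documented.** Aim 3 is exploratory and gives a direction without a size. Mild dispersion costs little: 0.05 gives 76% at 64 per group, and 80% with 71 per group followed for a full year. This stands, so the size of the loss is unknown and mild values belong in the range.
- **The Berg evidence is weak.** A score of 42 or less is also an entry criterion, so that cut-off cannot separate enrolled patients, and the gait-speed limit narrows the spread of risk further. This stands as a limit on the Berg evidence. Narrower eligibility still cannot make Var(rate) negative, and Aim 3 looks for differences inside the enrolled Delayed group.
- **An upper limit can add power in some models.** With the means held at 1.8 and 1.2, a Poisson truncated at 5 gives 80.7% and at 4 gives 84.3%; a binomial count with at most 12 falls gives 83.5%. The arithmetic is right, but the documents propose no such limit and do not argue that counts are more regular than Poisson.
- **The faller illustration is fragile.** Poisson at 1.2 per year already gives 70% fallers, and a high-risk cohort may exceed that. Agreed; the conclusion does not rest on it.
- **The consequence is limited.** The plan says it cannot quantify the gain, and a wide confidence interval would show the imprecision of a null result. That softens the risk of misreading but leaves an unsupported statement about the power of the primary analysis.

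**Conclusion.** The concern holds. The reason given for variance below Poisson leaves power at 78.6% for any cap of 6 falls or more, and the documents offer no other. The plan's premise that fall risk differs between patients points to variance above Poisson, so the favourable direction claimed is unsupported and probably reversed.

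Under the assumed negative binomial model, power at 64 per group falls from 79% to between 76% (dispersion 0.05) and 29% (dispersion 2); a dispersion of 0.25 costs about 13 points. With all 71 per group followed for a full year, power is below 80% from a dispersion of 0.1 upward. The size depends on a dispersion the documents do not give. The lack of support for the claim does not. Validity of the primary test is not in question.

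**What to change.** In the Power analysis paragraph of section 6, delete the two sentences claiming variance below Poisson and higher power, together with the remark that the gain cannot be quantified. State that the 80% figure assumes Poisson counts with no between-patient variation in fall rate within a group. Rerun the existing 10,000-run simulation with negative binomial counts over a stated dispersion range that includes mild values, for example 0.05 to 2, and report power and the detectable rate ratio at each value. If a source supports a particular dispersion, cite it.

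The cost is wording and one rerun with a different count distribution. The primary analysis and sample size need not change, but the stated power will look less favourable.
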